7.1 Data and Biospecimen Management

Data Management and Access:

The PI will be responsible for overseeing entry of data into a password-protected electronic system that complies with NIH security standards and NHLBI DIR policy, and for ensuring data accuracy, consistency and timeliness of entry. The PI, associate investigators/research nurses and/or a contracted data manager may assist with the data management efforts. All human subjects personally identifiable information (PII), as defined in accordance to the Health Insurance Portability and Accountability Act (HIPAA), eligibility and consent verification will be recorded in conformity with DIR policy. Primary and final analyzed data will have unique codes so that research data can be attributed to an individual human subject participant. Coded data may be sent to associate investigators and collaborators outside of the NIH with IRB approval; local institutional approval may be required. Data with subject personal identifiers may be sent to associate investigators and collaborators outside of the NIH only after approvals of both NHLBI and local IRBs or executed reliance agreement with NHLBI's IRB, or an extension of the NIH's FWA through an Individual Investigator Agreement.

Biospecimen Management:

Blood samples will be coded and stored in conformity with DIR Policy (e.g., BSI). Coded biospecimens may only be sent to collaborators outside of the NIH after, IRB approval in accordance with applicable NIH and DIR Policy for sharing research resources, including an executed material transfer agreement.

End of Study Procedures:

Data retained by the NHLBI will be stored in a password-protected database in conformity with NHLBI DIR policy until they are no longer of scientific value, as determined by the PI.

Breach of Confidentiality:

PI will report any breach of subject confidentiality or trial data to the clinical director and IRB per NIH policy, including NIH HRPP SOP 16 - Reporting Requirements for Unanticipated Problems, Adverse Events and Protocol Deviations.

7.2 Data Sharing and Future Use of Data

Data Sharing Plans:

Research data will not be shared with non-approved researchers. If data sharing becomes necessary it may occur after IRB review and approval or a determination from the NIH OHSRP.

Future Use of Biospecimens:

Following the termination of the study, biospecimens will be destroyed. If any future research on biospecimens is intended, an IRB review and approval will be submitted.

8. Monitoring of Subjects and Criteria for Withdrawal of Subjects

8.1 Stopping Rules for Subjects

- A single episode of severe gastrointestinal discomfort that in consultation with the physician is severe enough to discontinue the protocol
- Moderate gastrointestinal symptoms that persists for more than 5 consecutive days relating to the supplementation and as determined by contact with the investigator
- Pregnancy and breastfeeding
- Anaphylactic reaction due to consumption of the fish oil supplement

- New onset atrial fibrillation/flutter
- Major bleeding episode (CTCAE 4.0 grade III or IV)
- Subjects taking irregular use of fish oil capsules that in the opinion of the PI may compromise the data integrity.
 - Any other severe symptoms related to the study and as determined by contact with the physician.

Subjects who are found to be pregnant or wish to breastfeed during the study will automatically be withdrawn. A pregnancy screening will be done for all female volunteers at the first visit and subjects will be excluded from the study if pregnant. It is not known whether the oils used in this study are secreted in breast milk. It is therefore not advisable for any breastfeeding woman to participate in this study. However, if a subject becomes pregnant during this study, monitoring of the pregnancy will continue until conclusion of the pregnancy.

Unlikely but possible adverse effects of omega-3 supplements may include atrial fibrillation (risk less than one in a hundred persons). Patients that develop symptoms of atrial fibrillation (palpitations, rapid heart rate, fainting, shortness of breath, etc.) will be instructed to visit the emergency room and seek treatment immediately. In order to prevent any future events, participants with atrial fibrillation will be withdrawn from the study. Individuals that develop an allergy to fish or shellfish may experience an anaphylactic reaction from the supplement and will also be instructed to visit the emergency room immediately and will also be withdrawn from the study (risk believed to be less than one in a thousand persons not known to have fish or shellfish allergy).

9. Analysis of the Study

The primary outcome measures of this study will be differences between randomized groups in differences between treatment periods in changes from baseline to end of period in the plasma total cholesterol. Secondary outcome measurements will be changes in proteomics, lipoprotein particle number, HDL functional test (i.e. efflux study) composition and size. Each subject will serve as their own control.

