| 10.5 Evaluation of Benefits and Risks/Discomforts | 20 |
| 10.6 Protocol Consent Processes and Documents..... | 22 |
| 10.7 Patient Advocate | 22 |
| 11. Conflict of Interest | 22 |
| 12. Adverse Events, Deviations, and Unanticipated Problem Reporting..... | 23 |
| 12.1 Adverse events (AE) | 23 |
| 12.2 Serious Adverse Events (SAE) | 24 |
| 12.3 Protocol Deviations (PD) | 25 |
| 12.4 Unanticipated Problem (UP)..... | 25 |
| 13. Data and Safety Monitoring Plan..... | 26 |
| 14. Compensation..... | 27 |
| 15. References | 29 |
| 16. APPENDIX A: NIH INFORMATION SHEET ON STAFF RESEARCH PARTICIPATION (April 2016)..... | 32 |

1. Objectives

The overall objective is to elucidate LCMUFA-induced changes on lipoproteins and lipoprotein metabolism. In particular, we will focus on the effect of LCMUFA supplementation on the level of pro-atherogenic cardiovascular biomarkers, such as LDL-C and triglycerides, as well as on the level of anti-atherogenic biomarkers, such as HDL-C. This will be first accomplished by performing a small pilot study to determine the effect size of LCMUFA supplementation on lipoprotein parameters to assist in the design of a possible future larger clinical trial.

2. Introduction

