3.1 Overview

The study will be a prospective double-blinded randomized crossover study, with four clinical visits (Fig. 2). During the first visit, subjects will be screened by an exclusion/inclusion questionnaire and baseline clinical laboratory testing. If not excluded, subjects may also be assessed for vascular compliance by Cardio-ankle vascular index (CAVI) testing^{27, 28}. Exercise and diet changes will be followed by a nutritionist, using a 7-day food diary*.

17-H-0050: Effect of Fish Oil Enriched In Omega-11 Fatty Acid On Lipoprotein Metabolism In Adults
 PI: [name].
 Date: May 2, 2019
 Version: 5.0 (Amendment D)

Fig. 2. Study design

Eligible subjects will be randomized to take Control Fish Oil capsules (CFO - a mixture of sardine oil and oleic acid-rich olive oil) or LCMUFA-rich fish oil capsules produced from Saury fish (LCMUFA) as described in Table 3.

Table 3 Amount of fatty acids contained in each capsule

| mg/capsule(1g) | Control oil (1g) (sardine oil + olive oil) | LCMUFA-rich Saury oil (1g) |
|----------------|---|-------------------------------|
| EPA+DHA | 178 | 151 |
| LCMUFA | 7 | 252 |
| C18:1 | 390 | 51 |
| saturated | 124 | 198 |
| omega-6 | 82 | 36 |
| omega-3 | 222 | 237 |
| MUFA | 438 | 336 |

Each fish oil supplementation period will last a minimum of 8 weeks and subjects receiving CFO capsules will receive a daily approximate dose of 3g of total omega-3 fatty acids and approximately 5g of total MUFA (Table 4). Subjects will return for a second visit at the end of this study arm and will discontinue any study related supplements. After a washout period of 8-10 weeks, they will return for a third visit to start the second arm of the study for another 8 weeks minimum. In case of scheduling problems subjects will continue on supplementation up to 2 extra weeks. A fourth and last visit will take place at the end of this second study arm and subjects will discontinue any study related supplements. Blood samples, as well as stool samples (optional), will be collected on each visit for analysis. CAVI analysis may also take

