Re-screening Visit as applicable: Repeat laboratory values, including baseline research blood, may be needed to reassess eligibility within 40 days of a screening failure. If a subject is found ineligible, during or after the first visit, the 10 mL of research blood will be discarded.

Visit 2: Eight weeks after initiating the fish oil supplement (+ 2 weeks if needed) the subjects will return for their second visit. They will receive laboratory tests and pregnancy testing for females. A stool sample may be obtained, but it's optional. In addition, 10 mL of blood will be stored for research tests. The subject will have vital signs and Body Mass Index measured, will receive a diet and exercise assessment to determine their nutritional status, and a Cardio-Ankle Vascular Index (CAVI) test may be performed. If necessary, a brief physical examination may be performed, a pill count will also be performed to evaluate compliance. At the end of the 2nd visit, the subjects will be instructed to discontinue any fish oil supplementation for 8 weeks (+ 2 weeks, if necessary), during the wash-out period.

Visit 3: The third visit will occur 8 weeks (+ 2 weeks if needed) after visit #2 for a 2nd baseline measurement. At this visit, the subjects will receive laboratory tests and pregnancy testing for females. A stool sample may be obtained, but it's optional. In addition, 10 mL of blood will be stored for research tests. The subject will have vital signs and Body Mass Index measured may receive a diet and exercise assessment to determine their nutritional status, and a Cardio-Ankle Vascular Index (CAVI) test may be performed. If necessary, a brief physical examination may be performed. At the end of the 3rd visit, subjects will receive a 10 week supply of the second dietary supplement (CFO or LCMUFA capsules) and will be instructed to take 4 capsules, 3 times a day, after meals (total of 12 capsules a day), for 8 weeks (+2 weeks, if needed).

Visit 4: The fourth and final visit will occur 8-10 weeks after starting the second fish oil supplementation. Subjects will receive laboratory tests and a pregnancy testing for females. A

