Drug Interactions: Clinical studies have not been done to thoroughly examine the effect of sardine oil- or LCMUFA-rich fish oil supplement with anticoagulants. Patients receiving these fish oil supplements and an anticoagulant or other drug affecting coagulation should be monitored periodically (e.g., aspirin, NSAIDS, warfarin, coumarin).

Stability: LCMUFA or oleic acid-rich fish oil supplement will be maintained and distributed as directed by the supplement manufacturer to maximize maintenance and the quality of active and inactive ingredients in the supplement. Capsules will be initially assigned a 3 year expiration from time of manufacture. Ongoing stability studies will determine if this may be extended. Capsules are not to be frozen.

6. Laboratory Methods

Up to 40 mL of fasting blood will be collected at each visit to perform clinical or research tests. Clinical tests that may be used are listed below and will be performed at the NIH Clinical Center Department of Laboratory Medicine on the second floor of building 10 in the Clinical Center.

Clinical laboratory tests:

- Pregnancy testing
- Liver function test (ALT, AST, bilirubin)
- Uric acid
- Creatinine
- Creatinine kinase (CK)
- Insulin
- Fasting glucose
- Fibrinogen
- PT, PTT
- Whole blood aggregation

17-H-0050: Effect of Fish Oil Enriched In Omega-11 Fatty Acid On Lipoprotein Metabolism In Adults
PI: [name].
Date: May 2, 2019
Version: 5.0 (Amendment D)

- CBC
- hs-CRP
- HbA1C
- TSH
- CBC
- EKG

Clinical lipid and lipoprotein related tests:

- Lipid Panel (Total cholesterol, LDL-C, HDL-C, Triglyceride)
- Lipoprotein Profile (NMR)
- ApoA-I
- ApoB

In addition, we may also conduct some or all of the following research tests: PHA stimulation whole blood, LC-MS-based proteomics, GC-MS-based lipidomics, specific proteins/enzymes related to lipoprotein metabolism (CETP, PLTP, PON, LCAT, LPL), ApoC-II, apoC-III, apoA-V, PCSK9, cholesterol efflux studies, ex-vivo lipolysis study, fatty acid analysis of red blood cells, leptin, adiponectin, blood cell RNA expression, flow cytometry phenotyping of white blood cells, plasma cytokines.

Standard of care laboratory tests and procedures not listed above may be requested and will not be used for research purposes but will only be used to evaluate the patients' health.

7. Data and Biospecimen Management Plan

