9.1 Sample Size Determination

Sample Size Determination and Methods

The study is designed to be a pilot trial to determine the effect size of the LCMUFA-rich fish oil supplement for a possible future larger clinical trial. The sample size requested in this study is based on our experience on other studies, such as the Omega-3 Fish Oil study. We are requesting to enroll up to 100 subjects to obtain 20* evaluable subjects that complete the whole study, and will perform an interim analysis after 10 subjects have completed both arms in the study. The proteomic analysis makes this study practical and innovative. Based on the information gathered from other studies and on the NHLBI proteomics core experience, the analysis of ten subjects is a realistic number to meet our scientific goals. The interim analysis

will be performed only for proteomic changes, and the magnitude of proteomic change will result in the decision of study continuation. This will allow us to gather sufficient data to estimate changes that could justify a larger study.

* evaluable subjects are subjects that have completed the full time-line of the study (Figure 2), have collected stool specimens and thru the analysis of red cell membrane omega-3 fatty acids (RCM) are found to have taken and absorbed the supplement.*

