9.2 Statistical Analysis

Descriptive statistics will be calculated for all variables. A student's t-test will be used to compare the difference in mean changes between the baseline and the end of each arm period while accounting for period and group effects. Data of proteomics will be analyzed by paired student's t-test to identify proteins with statistically significant ($p < 0.05$) changes in normalized spectral counts, and an at least 1.3~1.5-fold will be considered as a physiologically meaningful change to continue the study. The study will be stopped if the changes are not statistically significant or the changes is smaller than 1.3-fold.

10. Human Subject Protection

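### Total cholesterol: adjusting for the difference between the two period baselines would usually be more precise than the planned (valid) change-from-baseline comparison, at almost no cost

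*Combined protocol and SAP*

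**What the plan says.** Section 9 defines the primary outcome as "differences between randomized groups in differences between treatment periods in changes from baseline to end of period in the plasma total cholesterol" and adds: "Each subject will serve as their own control". Section 9.2 assigns a Student's t-test "to compare the difference in mean changes between the baseline and the end of each arm period while accounting for period and group effects". Neither section names a baseline covariate.

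Both period baselines are measured. Section 3.2 schedules Visit 3 "after visit #2 for a 2nd baseline measurement", and under Section 6 "fasting blood will be collected at each visit to perform clinical or research tests". The second baseline follows the first supplement; Section 3.1 says: "After a washout period of 8-10 weeks, they will return for a third visit to start the second arm of the study".

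Section 9.1 calls the study a "pilot trial to determine the effect size of the LCMUFA-rich fish oil supplement for a possible future larger clinical trial", and Section 1 likewise describes a "small pilot study to determine the effect size of LCMUFA supplementation on lipoprotein parameters". The target is 20 evaluable completers. Sections 9.1 and 9.2 also provide a proteomics-only interim analysis after 10 completers, at which the study can stop.

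**The concern.** A crossover comparison differences each subject's two periods, which removes stable between-subject variation. Subtracting each period's baseline as well fixes at exactly 1 the slope relating the end-of-period difference to the baseline difference. If the true slope is well below 1, that over-corrects and adds noise from two extra measurements. Estimating the slope avoids this.

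The stake is precision. The pilot exists to supply an effect size and plans only 20 evaluable subjects, so precision available from blood already drawn is worth having.

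**Working it through.** **Inputs from the documents.** There are four fasting samples per subject: baseline and end of period 1 (X1, Y1) and of period 2 (X2, Y2). The target is 20 completers, with a possible stop at 10. No SD, correlation, effect size, power or allocation ratio is given for total cholesterol, so the figure of 20 cannot be reproduced.

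**Assumptions.** Equal allocation to the two sequences and, at first, equal variance at all visits. Write dX = X1 − X2, dY = Y1 − Y2, V for their common variance, and b for the slope of dY on dX.

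**Variances per subject**
- Change score: Var(dY − dX) = 2V(1 − b).
- Adjusted: V(1 − b²), times 1 + 1/(n − 4) for estimating the slope.
- Large-sample ratio: 2(1 − b)/(1 − b²) = 2/(1 + b).
- n = 20: the slope factor is 17/16, so the ratio is 1.88/(1 + b), with break-even at b = 15/17 = 0.88.
- n = 10: the slope factor is 7/6, so the ratio is 1.71/(1 + b), with break-even at b = 5/7 = 0.71.

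**Value of b.** It is 0 when all visits are equally correlated and r/2 under serial (AR) decay with correlation r between successive visits. With within-period correlation w and between-period correlation v, it is (w − v)/(1 − v).

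| Assumed correlations | b | Ratio, n = 20 | Ratio, n = 10 |
|---|---|---|---|
| all equal | 0 | 1.88 | 1.71 |
| AR 0.5, or w/v 0.85/0.8 | 0.25 | 1.51 | 1.37 |
| AR 0.8 | 0.40 | 1.34 | 1.22 |
| AR 0.9 | 0.45 | 1.30 | 1.18 |
| w/v 0.9/0.8 | 0.50 | 1.25 | 1.14 |
| w/v 0.9/0.7 | 0.67 | 1.13 | 1.03 |
| w/v 0.95/0.8 | 0.75 | 1.08 | 0.98 |
| w/v 0.95/0.6 | 0.875 | 1.00 | 0.91 |
| w/v 0.97/0.6 | 0.925 | 0.98 | 0.89 |

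Simulation at n = 20 (40,000 runs per case) agreed: 1.88 to 1.93 for equal correlations, 1.50, 1.34 and 1.31 for AR 0.5, 0.8 and 0.9, and 0.98 in the last row.

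**Unequal variances.** If the end-of-period SD is 15% below or above the baseline SD, the simulated n = 20 ratios are 2.26 or 1.63 (all equal at 0.8), 1.61 or 1.19 (AR 0.8), 1.38 or 1.02 (0.9/0.7), and 1.29 or 0.94 (0.95/0.6).

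**In mg/dL, at an assumed SD of 35.** The treatment effect is half the sequence contrast, so its SE is ½√[variance × (1/10 + 1/10)] = √(0.05 × variance). With all correlations 0.8, V = 2 × 35² × 0.2 = 490.
- Change score: √(0.05 × 980) = 7.0.
- Adjusted: √(0.05 × 490 × 17/16) = 5.1.

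Simulated mean 95% CI half-widths, change score against adjusted:
- all equal at 0.8: 14.5 v 10.6
- AR 0.8: 15.1 v 13.0
- 0.9/0.7: 10.3 v 9.7
- 0.95/0.6: 7.25 v 7.26

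**Carryover.** Let c be the residual LCMUFA-minus-control effect at Visit 3, with the sign of the true effect.
- Persisting unchanged to Visit 4: the change score is unbiased, and the adjusted estimate is pulled toward zero by (1 − b)c/2.
- Gone by Visit 4: the change score is exaggerated by c/2, the adjusted estimate by only bc/2.

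With an assumed effect of −10 and c = −4, for all equal at 0.8, AR 0.8 and 0.9/0.7 in turn:
- Persisting: adjusted −8.0, −8.8 and −9.4; change score −10.0 throughout.
- Gone: adjusted −10.0, −10.8 and −11.3; change score about −12.0 throughout.

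RMSE, change score v adjusted, was 7.0 v 5.5, 7.3 v 6.4 and 4.9 v 4.7 (persisting), and 7.3 v 5.1, 7.5 v 6.4 and 5.3 v 4.9 (gone).

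**The case against.** The strongest reply is that nothing is broken. Change from each period's own baseline, compared between sequences, is a standard crossover analysis and is unbiased under randomization without carryover. That stands: a reader who infers an error or an invalid test goes further than the documents allow.

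**The gain is assumed and may be small.** This also stands. A ratio of 1.88 requires Visit 1 to be no more correlated with Visit 2, 8 weeks later, than with Visit 4, at least 24 weeks later. Serial decay is easier to believe and gives about 1.3 to 1.5. Strong within-period correlation can remove the gain, and a stop at 10 completers makes a loss more likely.

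**Carryover that persists would favour the planned analysis.** True, but carryover that fades would favour the adjusted one, and the documents do not show which applies. This is a reason to report both.

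**It may be too late.** Section 10.6 says that, as of 2 May 2019, accrual has closed and only data analysis remains. Section 3.1 allows unblinding once a participant has finished both arms. The documents do not say whether cholesterol results by treatment have been seen, so the change has to be conditional on that.

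A reader might also infer that the pilot will report an effect twice its true size. With periods differenced as first minus second, the contrast in Section 9 does equal twice the LCMUFA-minus-control effect. But no section says the unhalved value will be reported, Section 9.2 can be read as already on the treatment-effect scale, and halving leaves the p-value unchanged. This is a missing detail and not a fault.

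**Conclusion.** This is a cheap improvement and not a correction. At n = 20 the adjusted estimate is usually more precise, with a variance ratio most plausibly about 1.3 to 1.5, at most about 1.9 with equal variances, and 1.0 or slightly less when b is near or above 0.88. Allowing the SD to differ by 15% between baseline and end of period widens the range to about 0.94 to 2.26. With 10 completers it runs from about 0.9 to 1.7 under equal variances.

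Every figure rests on assumed correlations, SDs and equal allocation. The algebra and the direction of the usual gain are secure; the size of the gain in this trial is unknown.

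**What to change.** **If total-cholesterol results by treatment are still unseen**, amend Sections 9 and 9.2 in a dated, documented change:
- Regress (end of period 1 minus end of period 2) on sequence and (baseline 1 minus baseline 2). The intercept absorbs the period effect.
- Report half the sequence contrast, LCMUFA-first minus CFO-first, as the LCMUFA-minus-CFO effect with a 95% CI.
- Report the change-score estimate as a sensitivity analysis.

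**If those results have been seen**, keep the change score as primary and label the adjusted estimate post hoc.

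**Optional clarification in either case:** state the direction of differencing, the halving, and whether change is absolute (mg/dL), percent or log.

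**Cost:** wording and one degree of freedom, with no new samples or visits. The risks are a small loss of precision if b is high or only 10 subjects complete, and a bias toward zero of (1 − b)c/2 if carryover with the sign of the effect persists to Visit 4. Against that, the change score carries the larger bias, c/2, if carryover has gone by then.

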9.1 Sample Size Determination

Sample Size Determination and Methods

The study is designed to be a pilot trial to determine the effect size of the LCMUFA-rich fish oil supplement for a possible future larger clinical trial. The sample size requested in this study is based on our experience on other studies, such as the Omega-3 Fish Oil study. We are requesting to enroll up to 100 subjects to obtain 20* evaluable subjects that complete the whole study, and will perform an interim analysis after 10 subjects have completed both arms in the study. The proteomic analysis makes this study practical and innovative. Based on the information gathered from other studies and on the NHLBI proteomics core experience, the analysis of ten subjects is a realistic number to meet our scientific goals. The interim analysis

will be performed only for proteomic changes, and the magnitude of proteomic change will result in the decision of study continuation. This will allow us to gather sufficient data to estimate changes that could justify a larger study.

* evaluable subjects are subjects that have completed the full time-line of the study (Figure 2), have collected stool specimens and thru the analysis of red cell membrane omega-3 fatty acids (RCM) are found to have taken and absorbed the supplement.*

